#### 5.4 ASSESSMENT OF BIOMARKER(S)

**Trial Protocol** 

Not applicable.

c34388550-04

#### 5.5 BIOBANKING

Not applicable.

#### 5.6 OTHER ASSESSMENTS

#### 5.7 APPROPRIATENESS OF MEASUREMENTS

All measurements performed during this trial are standard measurements and will be performed in order to monitor subjects' safety and to determine pharmacokinetic parameters in an appropriate way. The scheduled measurements will allow monitoring of changes in vital signs, standard laboratory values, and ECG parameters that might occur as a result of administration of trial medication. The safety assessments are standard, are accepted for evaluation of safety and tolerability of an orally administered drug, and are widely used in clinical trials. The pharmacokinetic parameters and measurements outlined in Section 5.3 are generally used assessments of drug exposure.

**c34388550-04** Trial Protocol Page 54 of 75

Proprietary confidential information © 2021 Boehringer Ingelheim International GmbH or one or more of its affiliated companies

#### 6. INVESTIGATIONAL PLAN

#### 6.1 VISIT SCHEDULE

Exact times of measurements outside the permitted time windows will be documented. The acceptable time windows for screening and the end of trial examination are provided in the Flow Chart.

Study measurements and assessments scheduled to occur 'before' trial medication administration on Day 1 are to be performed and completed within a 3 h-period prior to the trial drug administration.

The acceptable deviation from the scheduled time for vital signs, ECG, and laboratory tests will be  $\pm$  15 min for the first 4 h after trial drug administration and  $\pm$  30 min thereafter. Starting from 48 h post-dose a deviation from the scheduled time for vital signs, ECG and laboratory tests of  $\pm$ 120 min is acceptable.

If several activities are scheduled at the same time point in the Flow Chart, blood sampling, vital signs, and 12-lead ECG should be the first and meal the last activity. Furthermore, if several measurements including venipuncture are scheduled for the same time, venipuncture should be the last of the measurements due to its inconvenience to the subject and possible influence on physiological parameters.

For planned individual plasma concentration sampling times refer to the Flow Chart. While these nominal times should be adhered to as closely as possible, the actual sampling times will be recorded and used for the determination of pharmacokinetic parameters.

If a subject misses an appointment, it will be rescheduled if possible. The relevance of measurements outside the permitted time windows will be assessed no later than at the Report Planning Meeting.

#### 6.2 DETAILS OF TRIAL PROCEDURES AT SELECTED VISITS

#### 6.2.1 Screening period

After having been informed about the trial, all subjects will provide written informed consent in accordance with GCP and local legislation prior to enrolment in the study.

For information regarding laboratory tests (including drug and virus screening), ECG, vital signs, and physical examination, refer to Sections 5.2.

#### **6.2.2** Treatment periods

Each subject is expected to participate in 2 treatment periods. At least 8 days will separate drug administrations in the first and second treatment periods.

On Day 1 of each treatment period, study participants will be admitted to the trial site and kept under close medical surveillance for at least 48 h following drug administration. The subjects will then be allowed to leave the trial site after formal assessment and confirmation of their fitness. On all other study days, subjects will be treated in an ambulatory fashion.

Page 55 of 75

Proprietary confidential information © 2021 Boehringer Ingelheim International GmbH or one or more of its affiliated companies

For details on time points and procedures for collection of plasma samples for PK analysis, refer to Flow Chart and Section 5.3.2.

The safety measurements performed during the treatment period are specified in Section 5.3 of this protocol and in the Flow Chart. For details on times of all other trial procedures, refer to the Flow Chart. AEs and concomitant therapy will be assessed continuously from screening until the end of trial examination.

#### 6.2.3 Follow-up period and trial completion

For AE assessment, laboratory tests, recording of ECG and vital signs, and physical examination during the follow-up period, see Sections 5.2.2 to 5.2.5. Subjects who discontinue treatment before the end of the planned treatment period should undergo the EoTrial Visit.

All abnormal values (including laboratory parameters) that are assessed as clinically relevant by the investigator will be monitored using the appropriate tests until a return to a medically acceptable level is achieved. (S)AEs persisting after a subject's EoTrial Visit must be followed until they have resolved, have been sufficiently characterised, or no further information can be obtained.

34388550-04 Trial Protocol Page 56 of 75

Proprietary confidential information © 2021 Boehringer Ingelheim International GmbH or one or more of its affiliated companies

# 7. STATISTICAL METHODS AND DETERMINATION OF SAMPLE SIZE

#### 7.1 STATISTICAL DESIGN – MODEL

The main objective of this trial is to investigate the relative bioavailability of 30 mg of BI 1595043 in the fed state (Test, T) compared with 30 mg of BI 1595043 in the fasting state (Reference, R) following oral administration on the basis of the primary and secondary pharmacokinetic endpoints, as listed in Section 2.1.2 and 2.1.3. The trial is designed to allow intra-subject comparisons and will be evaluated statistically by use of a linear model for logarithmically transformed PK endpoints.

The assessment of safety and tolerability is a further objective of this trial, and will be evaluated by descriptive statistics for the parameters specified in Section 2.2.2.2.

#### 7.2 NULL AND ALTERNATIVE HYPOTHESES

The relative bioavailability of BI 1595043 in the fed state compared with BI 1595043 in the fasted state will be estimated by the ratios of the geometric means (test/reference), and their corresponding 2-sided 90% confidence intervals (CIs) will be provided. This method corresponds to the two one-sided t-test procedure, each at the 5% significance level. Since the main focus is on estimation and not testing, a formal hypothesis test and associated acceptance range is not specified.

#### 7.3 PLANNED ANALYSES

#### Analysis sets

Statistical analyses will be based on the following analysis sets:

- Treated set (TS): The treated set includes all subjects who were randomized and treated with at least one dose of study drug. The treated set will be used for safety analyses.
- Pharmacokinetic parameter analysis set (PKS): This set includes all subjects in the treated set (TS) who provide at least one PK endpoint that was defined as primary or secondary and was not excluded due to a protocol violation relevant to the evaluation of PK or due to PK non-evaluability (as specified in the following subsection 'Pharmacokinetics'). Thus, a subject will be included in the PKS, even if he/she contributes only one PK parameter value for one period to the statistical assessment. Descriptive and model based analyses of PK parameters will be based on the PKS.

Adherence to the protocol will be assessed by the trial team. Important protocol deviation (iPD) categories will be suggested in the iPD specification file, iPDs will be identified no later than in the Report Planning Meeting, and the iPD categories will be updated as needed.

c34388550-04 Trial Protocol

Proprietary confidential information © 2021 Boehringer Ingelheim International GmbH or one or more of its affiliated companies

#### Pharmacokinetics

The pharmacokinetic parameters listed in Section 2.1 for BI 1595043 will be calculated according to the relevant SOP of the Sponsor (001-MCS-36-472).

Plasma concentration data and parameters of a subject will be included in the statistical pharmacokinetic (PK) analyses if they are not flagged for exclusion due to a protocol deviation relevant to the evaluation of PK (to be decided no later than in the Report Planning Meeting) or due to PK non-evaluability (as revealed during data analysis, based on the criteria specified below). Exclusion of a subject's data will be documented in the CTR.

Relevant protocol deviations may be

- Incorrect trial medication taken, i.e. the subject received at least one dose of trial medication the subject was not assigned to
- Incorrect dose of trial medication taken
- Use of restricted medications

Plasma concentrations and/or parameters of a subject will be considered as non-evaluable, if for example

- The subject experienced emesis that occurred at or before two times median t_{max} of the respective treatment (Median t_{max} is to be determined excluding the subjects experiencing emesis),
- The subject experiences emesis at any time during the labelled dosing interval.
- A predose concentration is >5% C_{max} value of that subject
- Missing samples/concentration data at important phases of PK disposition curve

Plasma concentration data and parameters of a subject which is flagged for exclusion will be reported with its individual values but will not be included in the statistical analyses. Descriptive and inferential statistics of PK parameters will be based on the PKS.

Only concentration values within the validated concentration range and actual sampling times will be used for the calculation of pharmacokinetic parameters. Concentrations used in the pharmacokinetic calculations will be in the same format provided in the bioanalytical report, (that is, to the same number of decimal places provided in the bioanalytical report).

#### 7.3.1 Primary endpoint analyses

#### Primary analyses

The statistical model used for the analysis of the primary endpoints will be an analysis of variance (ANOVA) model on the logarithmic scale. That is, the PK endpoints will be log-transformed (natural logarithm) prior to fitting the ANOVA model. This model will include effects accounting for the following sources of variation: sequence, subjects within sequences, period and treatment. The effect 'subjects within sequences' will be considered as random, whereas the other effects will be considered as fixed. The model is described by the following equation:

Page 57 of 75

Proprietary confidential information © 2021 Boehringer Ingelheim International GmbH or one or more of its affiliated companies

$$y_{ijkm} = \mu + \zeta_i + s_{im} + \pi_j + \tau_k + e_{ijkm}$$
, where

 $y_{ijkm}$  = logarithm of response measured on subject m in sequence i receiving treatment k in period j,

 $\mu$  = the overall mean,

 $\zeta_i$  = the ith sequence effect, i = 1, 2,

 $s_{im}$  = the effect associated with the  $m^{th}$  subject in the  $i^{th}$  sequence,  $m = 1, 2, ..., n_i$ 

 $\pi_j$  = the jth period effect, j = 1, 2,

 $\tau_k$  = the kth treatment effect, k = 1, 2,

 $e_{ijkm}$  = the random error associated with the  $m^{th}$  subject in sequence i who received treatment k in period j.

where  $s_{im} \sim N(0, \sigma_B^2)$  i.i.d.,  $e_{ijkm} \sim N(0, \sigma_W^2)$  i.i.d. and  $s_{im}$ ,  $e_{ijkm}$  are independent random variables.

Point estimates for the ratios of the geometric means (test/reference) for the primary endpoints (see Section 2.1) and their two-sided 90% confidence intervals (CIs) will be provided.

For each endpoint, the difference between the expected means for log(T)-log(R) will be estimated by the difference in the corresponding adjusted means (Least Squares Means). Additionally their two-sided 90% confidence intervals will be calculated based on the residual error from the ANOVA and quantiles from the t-distribution. These quantities will then be back-transformed to the original scale to provide the point estimate and 90% CIs for each endpoint.

#### 7.3.2 Secondary endpoint analyses

The secondary endpoints (refer to Section 2.1.3) will be calculated according to the BI SOP 'Standards and processes for analyses performed within Clinical Pharmacokinetics/ Pharmacodynamics' (001-MCS-36-472) and will be assessed statistically using the same methods as described for the primary endpoints.

Page 59 of 75

Proprietary confidential information © 2021 Boehringer Ingelheim International GmbH or one or more of its affiliated companies

#### 7.3.4 Safety analyses

Safety will be analysed based on the assessments described in Section 2.2.2.2. All treated subjects (TS, refer to Section 7.2) will be included in the safety analysis. Safety analyses will be descriptive in nature and based on BI standards. No hypothesis testing is planned.

For all analyses, the treatment actually administered (= treatment at onset) to the subject will be used (any deviations from the randomised treatment will be discussed in the minutes of the Report Planning Meeting).

Treatments will be compared in a descriptive way. Tabulations of frequencies/proportions will be used to evaluate categorical (qualitative) data, and tabulations of descriptive statistics will be used to analyse continuous (quantitative) data.

Measurements (such as ECG, vital signs, or laboratory parameters) or AEs will be assigned to treatments (see Section 4.1) based on the actual treatment at the planned time of the measurement or on the recorded time of AE onset (concept of treatment emergent AEs). Therefore, measurements planned or AEs recorded prior to first intake of trial medication will be assigned to the screening period, those between first trial medication intake and end of REP (see Section 1.2.6) will be assigned to the treatment period. Events occurring after the REP but prior to next intake or end of trial termination date will be assigned to 'follow-up'. In case of two or more treatments, the follow-up will be summarized according to the previous treatment. These assignments including the corresponding time intervals will be defined in detail in the TSAP. Note that AEs occurring after the last per protocol contact but entered before final database lock will be reported to Pharmacovigilance only and will not be captured in the trial database.

Additionally, further treatment intervals (analysing treatments) may be defined in the TSAP in order to provide summary statistics for time intervals, such as combined treatments, ontreatment totals, or periods without treatment effects (such as screening and follow-up intervals).

Adverse events will be coded using the Medical Dictionary for Regulatory Activities (MedDRA). Frequency, severity, and causal relationship of AEs will be tabulated by treatment, system organ class, and preferred term. SAEs, AESIs (see Section 5.2.7.1), and other significant AEs (according to ICH E3) will be listed separately.

Previous and concomitant therapies will be presented per treatment group without consideration of time intervals and treatment periods.

Laboratory data will be compared to their reference ranges. Values outside the reference range as well as values defined as possibly clinically significant will be highlighted in the listings. Additionally, differences from baseline will be evaluated.

34388550-04 Trial Protocol Page 60 of 75

Proprietary confidential information © 2021 Boehringer Ingelheim International GmbH or one or more of its affiliated companies

Vital signs or other safety-relevant data will be assessed with regard to possible on-treatment changes from baseline.

Relevant ECG findings will be reported as AEs.

#### 7.4 INTERIM ANALYSES

No interim analysis is planned.

#### 7.5 HANDLING OF MISSING DATA

#### **7.5.1** Safety

It is not planned to impute missing values for safety parameters.

#### 7.5.2 Pharmacokinetics

Handling of missing PK data will be performed according to the relevant Corporate Procedure (001-MCS-36-472).

PK parameters that cannot be reasonably calculated based on the available drug concentration-time data will not be imputed.

#### 7.6 RANDOMISATION

Subjects will be randomised to one of the 2 treatment sequences in a 1:1 ratio. The block size will be documented in the CTR.

The sponsor will arrange for the randomisation as well as packaging and labelling of trial medication. The randomisation list will be generated using a validated system that uses a pseudo-random number generator and a supplied seed number so that the resulting allocation is both reproducible and non-predictable.

The randomisation list will contain additional blocks to allow for subject replacement (refer to Section 3.3.5).

#### 7.7 DETERMINATION OF SAMPLE SIZE

It is planned to enter a total of 14 subjects in the trial, because this sample size is considered sufficient to achieve the aims of this exploratory trial. With this sample size, the following precision in estimating the ratio of geometric means (test/reference) can be expected with 95% probability. Precision is defined as the ratio of upper CI limit to the relative BA estimate. Note that the precision is independent of the actual ratio of geometric means.

Based on the previous SRD trial (see Section 1.2.5.2), the intra-individual coefficient of variation (gCV) for BI 1595043 is assumed to be roughly 23%.

For various assumptions around the gCV of 23%, Table 7.7: 1 provides an overview of the achievable precision for estimating the ratio of geometric means (test/reference). For

c34388550-04 Trial Protocol Proprietary confidential information © 2021 Boehringer Ingelheim International GmbH or one or more of its affiliated companies

structives may make a the expected 0.00% confidence intervals are displayed for a value of

illustrative purposes, the expected 90% confidence intervals are displayed for a value of 100% for the ratio T/R of geometric means.

Table 7.7: 1 Precision that can be expected with 95% probability and illustrative two-sided 90% confidence intervals around the ratio of geometric means (T/R) for different gCVs and sample sizes N in a 2x2 crossover trial

gCV [%]	N	Precision**	Ratio [%]*	Lower CL [%]	Upper CL [%]
	10	1.258		79.51	125.77
20	12	1.219	100	82.01	121.93
20	14	1.193	100	83.81	119.31
	16	1.174		85.18	117.40
	10	1.301	100	76.88	130.07
23	12	1.255		79.67	125.52
23	14	1.224		81.67	122.44
	16	1.202		83.20	120.19
	10	1.360	100	73.56	135.95
27	12	1.304		76.68	130.42
27	14	1.267	100	78.94	126.69
	16	1.240		80.67	123.97

^{*}Ratio of geometric means (test/reference) for a PK endpoint is defined by  $\exp(\mu_T)/\exp(\mu_R)$ .

The expected 90% confidence interval limits in the table were derived by

CI limit_{upper,lower} = 
$$exp(ln(\theta) \pm \omega)$$
,

with  $\theta$  being the ratio (T/R) on original scale and  $\omega$  the distance from the estimate  $\theta$  to either confidence interval limit on the log-scale, which was obtained from the achievable precision on the original scale.

The calculation was performed as described by Julious [R11-5230] using R Version 4.0.2.

^{**}Defined as ratio of upper CL and relative BA estimate.

c34388550-04 Trial Protocol Page 62 of 75

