## 1.2.5 Clinical experience in humans

The first in human study SRD study 1445-0001 is ongoing at the time of current 1445-0011 clinical trial protocol preparation. The SRD study consists of 7 original dose groups of 8 subjects each that have been completed. These include dose levels 1 mg, 3 mg, 6 mg, 12 mg, 25 mg, 50 mg, and 90 mg of BI 1595043, administered as oral solution, with 6 subjects in each dose group assigned to active treatment and 2 subjects assigned to placebo. The SRD clinical trial protocol is being amended to add one additional dose level of 160 mg of BI 1595043 at the time of preparation of 1445-0011 clinical trial protocol.

At this point in the clinical trial, BI 1595043 has been administered to 42 healthy male subjects as oral single doses of oral solution within 7 dose groups. Additionally, 14 healthy male subjects have received matching placebo.

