#### 1.3 RATIONALE FOR PERFORMING THE TRIAL

The trial is conducted to gain information about the effect of food on the relative bioavailability of the BI 1595043 tablet formulation. The data obtained in this study will support the optimization of trial design in upcoming clinical studies, and may be crucial information for formulation development.

Dose selection of 30 mg of BI 1595043 is based on the assumption to include a potential therapeutic dose (see Section 1.2.4).

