#### 1.4.4 Overall assessment

BI 1595043, a first-in-class vanin inhibitor, has been thus far administered to 42 healthy subjects in the preceding FIH SRD study. This is the third trial with BI 1595043 and the first with administration under fed condition. Despite the novelty of the target, non-clinical safety data in relevant animal species, preliminary clinical data obtained in 1445-0001 SRD study, the inhibitory mode of action as well as the comprehensive risk assessment suggest that BI 1595043 is not a high-risk compound and support the application of BI 1595043 under fed condition in this trial.

Based on the risk mitigation strategy, healthy subjects should not be exposed to undue risks by the intake of BI 1595043. Healthy volunteers are not expected to have any direct benefit from participation in this trial, as is usually the case in Phase I studies. Considering the high medical need for novel, effective and safe treatment for CD, it is believed that the benefit of this trial outweighs the potential risks and justifies exposure of healthy volunteers to BI 1595043.

c34388550-04 Trial Protocol Page 31 of 75

Proprietary confidential information © 2021 Boehringer Ingelheim International GmbH or one or more of its affiliated companies

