7. PLANNED ANALYSIS

Safety analysis (refer to [Section 7.8](#)) will be performed by [REDACTED] and will be presented in Sections 15.1 to 15.4 of the CTR and in Appendix 16.2 and 16.1.13.1.

Inferential statistical analyses of PK endpoints (refer to [Section 7.4](#) and [Section 7.5.2](#)) will also be performed by [REDACTED] and will be presented in Section 15.5 of the CTR and in Appendix 16.1.13.3.

Descriptive data analysis of PK endpoints and concentrations will be performed by the [REDACTED] at [REDACTED] and will be presented in Section 15.6 of the CTR.

The format of the listings and tables will follow the BI standards (see BI-KMED-BDS-HTG-0045 ([6](#)) with the exception of those generated for PK-calculations following BI standards for PK/PD analysis ([7](#)).

The individual values of all subjects will be listed, sorted by treatment sequence, subject number and visit. The listings will be included in Appendix 16.2 of the CTR.

For End-Of-Text (EoT) tables, the set of summary statistics is:

N	number non-missing observations
Mean	arithmetic mean
SD	standard deviation
Min	minimum
Median	median
Max	maximum

For analyte concentrations, the following descriptive statistics will additionally be calculated:

CV	arithmetic coefficient of variation
gMean	geometric mean
gCV	geometric coefficient of variation

For PK parameters, the following descriptive statistics will additionally be calculated:

CV	arithmetic coefficient of variation
gMean	geometric mean
gCV	geometric coefficient of variation
P10	10th percentile
Q1	1st quartile
Q3	3rd quartile
P90	90th percentile

The data format for descriptive statistics of concentrations will be identical to the data format of the respective concentrations. The descriptive statistics of PK parameters will be calculated

using the individual values with the number of decimal places as provided by the evaluation program. Then the individual values as well as the descriptive statistics will be reported with three significant digits in the CTR.

Tabulations of frequencies for categorical data will include all possible categories and will display the number of observations in a category as well as the percentage (%) relative to the respective treatment group (unless otherwise specified, all subjects in the respective subject set whether they have non-missing values or not).

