7.4.1 Primary analysis of the primary endpoints

Section 7.3.1 of the CTP:

The statistical model used for the analysis of the primary endpoints will be an analysis of variance (ANOVA) model on the logarithmic scale. That is, the PK endpoints will be log-transformed (natural logarithm) prior to fitting the ANOVA model. This model will include effects accounting for the following sources of variation: sequence, subjects within sequences, period and treatment. The effect 'subjects within sequences' will be considered as random, whereas the other effects will be considered as fixed. The model is described by the following equation:

$$\begin{aligned} y_{ijkm} &= \mu + \zeta_i + s_{im} + \pi_j + \tau_k + e_{ijkm}, \text{ where} \\ y_{ijkm} &= \text{logarithm of response measured on subject } m \text{ in sequence } i \text{ receiving} \\ &\quad \text{treatment } k \text{ in period } j, \\ \mu &= \text{the overall mean,} \\ \zeta_i &= \text{the } i^{\text{th}} \text{ sequence effect, } i = 1, 2 \\ s_{im} &= \text{the effect associated with the } m^{\text{th}} \text{ subject in the } i^{\text{th}} \text{ sequence, } m = 1, 2, \dots, n_i \end{aligned}$$

π_j = the j^{th} period effect, $j = 1, 2$
 τ_k = the k^{th} treatment effect, $k = 1, 2$
 e_{ijkm} = the random error associated with the m^{th} subject in sequence i who received treatment k in period j .

where $s_{im} \sim N(0, \sigma_B^2)$ i.i.d., $e_{ijkm} \sim N(0, \sigma_W^2)$ i.i.d. and s_{im}, e_{ijkm} are independent random variables.

Point estimates for the ratios of the geometric means (test/reference) for the primary endpoints (see CTP Section 2.1) and their two-sided 90% confidence intervals (CIs) will be provided.

For each endpoint, the difference between the expected means for $\log(T)$ - $\log(R)$ will be estimated by the difference in the corresponding adjusted means (Least Squares Means). Additionally their two-sided 90% confidence intervals will be calculated based on the residual error from the ANOVA and quantiles from the t -distribution. These quantities will then be back-transformed to the original scale to provide the point estimate and 90% CIs for each endpoint.

The implementation for this analysis will be accomplished by using the CSD macros based on PKS. The following SAS code can be used:

```
PROC MIXED DATA=indata METHOD=REML;  
  CLASS subject treatment sequence period;  
  MODEL logpk = treatment sequence period / DDFM=KR;  
  RANDOM subject(sequence);  

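### Does the 23% planning gCV need changing because the section it cites reports only across-subject variability?

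*Protocol*

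**What the plan says.** Protocol Section 7.7 plans for 14 subjects in a 2x2 crossover and describes the trial as exploratory. Its variability input reads "Based on the previous SRD trial (see Section 1.2.5.2), the intra-individual coefficient of variation (gCV) for BI 1595043 is assumed to be roughly 23" per cent. Table 7.7: 1 then gives the precision (upper 90% confidence limit divided by the estimate) expected with 95% probability, for gCVs of 20%, 23% and 27% and for 10 to 16 subjects. At 23% and 14 subjects it is 1.224.

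On the SRD trial, Protocol Section 1.2.5 says that "BI 1595043 has been administered to 42 healthy male subjects as oral single doses of oral solution within 7 dose groups", "with 6 subjects in each dose group assigned to active treatment and 2 subjects assigned to placebo". Section 1.2.5.2 gives geometric means and gCVs by dose group.

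Protocol Section 7.2 says that "a formal hypothesis test and associated acceptance range is not specified". SAP Section 7.4.1 specifies the ratios of geometric means "and their two-sided 90% confidence intervals (CIs) will be provided", computed from the residual error of the fitted model. SAP Section 7 lists further descriptive summaries, including the gCV, under the line "For PK parameters, the following descriptive statistics will additionally be calculated".

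**The concern.** The label and the citation do not fit together. A within-subject gCV needs at least two measurements per subject. In the SRD trial, 7 groups of 6 active subjects make 42, which is the whole active population, so each subject had one active dose. Table 1.2.5.2: 2 can therefore give only total variability. A reader who follows the citation finds neither the type of variance named in Section 7.7 nor the number 23 for a primary endpoint. Section 7.7 also does not say whether 23% refers to AUC0-tz or Cmax, which differ in that table.

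Two things could be at stake. If the planning value were badly wrong, the expected precision and the choice of 14 subjects would rest on nothing. And since Section 1.3 says "The data obtained in this study will support the optimization of trial design in upcoming clinical studies", a total gCV labelled as intra-individual might be reused as a within-subject value when a later study is sized, the more so because the visible SAP text does not name the within-subject gCV as an output.

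**Working it through.** **1. Reproduce the plan's figure.** Inputs from Section 7.7: gCV 0.23, N = 14, two-sided 90% interval, 95% probability. Residual degrees of freedom are N − 2 = 12.

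- Within-subject log variance: s² = ln(1 + 0.23²) = 0.05155
- Variance of the treatment difference: 2s²/N = 2 × 0.05155/14 = 0.007364
- Inflation for 95% assurance: χ²(0.95; 12)/12 = 21.026/12 = 1.752
- Half-width on the log scale: t(0.95; 12) × √(0.007364 × 1.752) = 1.7823 × 0.11359 = 0.2025
- Precision: exp(0.2025) = 1.224, giving limits of 81.67% and 122.44% around 100%

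This matches the printed row, and the same formula reproduces all 12 rows of Table 7.7: 1.

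**2. What the cited table contains.** In Table 1.2.5.2: 2 the AUC0-tz gCVs run from 14.3% to 27.8% (six groups; not calculated at 90 mg) and the Cmax gCVs from 10.9% to 27.1% (seven groups). None is 23%. One possible origin is a blend of the two endpoints at 25 mg, the dose nearest 30 mg:

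- AUC0-tz 20.1%: ln(1 + 0.201²) = 0.03961
- Cmax 26.2%: ln(1 + 0.262²) = 0.06639
- Mean 0.05300, so gCV = √(exp(0.05300) − 1) = 23.3%; the arithmetic mean is 23.15%

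This is a conjecture; the protocol does not state it.

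**3. Sensitivity.** Assumption: the SRD gCVs are read as if they were within-subject. Precision at N = 14:

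| Source | gCV | Precision |
|---|---|---|
| AUC0-tz, all groups pooled on the log-variance scale | 20.4% | 1.198 |
| Cmax, all groups pooled on the log-variance scale | 20.9% | 1.203 |
| AUC0-tz, 25 mg and 50 mg | 20.1%, 20.2% | 1.194, 1.195 |
| Cmax, 25 mg and 50 mg | 26.2%, 27.1% | 1.258, 1.268 |
| 25 mg blend | 23.3% | 1.228 |
| Printed rows of Table 7.7: 1 | 20%, 23%, 27% | 1.193, 1.224, 1.267 |

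The results fall on both sides of 1.224, and the printed grid covers them to within 0.001.

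**4. What depends on 23%.** It enters only Table 7.7: 1. There is no power, margin or required precision that a different value would cause the trial to miss. The reported intervals use the observed residual variance.

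**5. Later use.** The within-subject gCV can be recovered from the reported results. With 14 completers in balanced sequences, s² = (N/2) × [ln(upper limit/estimate)/t(0.95; 12)]². Check: at gCV 23% without the assurance factor, the upper limit divided by the estimate is 1.165, so s² = 7 × (0.1530/1.7823)² = 0.0516 and gCV = √(exp(0.0516) − 1) = 23%.

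**The case for a change.** The strongest case for acting is that Section 7.7 is the only stated basis for the expected precision, its citation does not contain what it names, and two sentences would repair it. Naming the endpoints would also show something the single figure hides: on the SRD values at 25 and 50 mg, Cmax sits near the 27% row and AUC0-tz near the 20% row. One further SAP line reporting the within-subject gCV would give later planners the value directly.

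The mismatch of label and table stands, and so does the missing endpoint. The rest is weaker. Section 7.7 says the assumption is based on the SRD trial, not that 23% is printed in the table. The SRD data also fed a population PK model (Sections 1.2.4 and 1.2.5.2), and Section 1.4.4 says "This is the third trial with BI 1595043 and the first with administration under fed condition", so a within-subject source may exist outside the visible text. No such value is shown, which leaves the origin unknown; it does not establish that 23% is a total gCV. Replacement wording that called it one would put a guess into the protocol as the sponsor's statement.

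The extra SAP output would change no estimate or interval. The sponsor's standard macros may already print it, and step 5 shows how to recover it. Nothing in the documents suggests that a later planner would prefer this assumption to the trial's own data.

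**Conclusion.** No change to the plan is needed. The observation is right as far as it goes: the cited gCVs are across-subject, and the source and endpoint of the 23% are not stated. That is a gap in documentation. The 23%, the precision of 1.224, Table 7.7: 1 and the 14 subjects all stand, and no estimate, interval or conclusion would differ.

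Across the readings tried above, precision at 14 subjects ranges from 1.194 to 1.268, against printed rows of 1.193 to 1.267. If the figure did come from total gCVs, that would normally err on the safe side, because total variance includes within-subject variance. This is not a strict bound: each SRD group had only 6 active subjects, and that trial gave an oral solution, whereas this one gives tablets with and without food.

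The conclusion rests on one active dose per SRD subject, which follows from the counts in Section 1.2.5, and on the trial remaining an estimation exercise without an acceptance range. If a precision target or an equivalence margin were added later, the source of the planning gCV would matter and would have to be stated by endpoint.
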